7.2 OUTCOMES

7.2.1 Primary outcomes

➤ Incidence rate of adverse events in patients with COPD treated with Tio+Olo

List of adverse events:

For acute, potentially recurrent events, including COPD exacerbations listed below, all subjects will be evaluated, regardless of whether such events occurred during the one-year baseline period.

- Respiratory tract disorders
 - 1. Nasopharyngitis
 - 2. Pneumonia
 - 3. COPD exacerbation
- Gastrointestinal disorders
 - 1. Constipation
 - 2. Diarrhoea
- Urinary disorders
 - 1. Urinary retention
 - 2. Urinary tract infection
- Immune system
 - 1. Urticaria

Statistical and Epidemiological Analysis Plan (SEAP) for Non-Interventional Studies (NIS) Template

c40431892-01 Page 10 of 38

Proprietary confidential information © 2022 Boehringer Ingelheim International GmbH or one or more of its affiliated companies

2. Rash

For chronic conditions listed below, subjects who had diagnosis of the condition during the one-year baseline period will be excluded from the incidence of adverse event analysis.

- Cardiovascular disorders
 - 1. Arrhythmia
 - 2. Myocardial ischemia
 - 3. Supraventricular tachycardia
- Ophthalmic disorders
 - 1. Glaucoma
- Serious Adverse Event (SAE)
 - 1. Nonfatal myocardial infarction
 - 2. Nonfatal stroke (hemorrhagic stroke, ischemic stroke and acute cerebrovascular disease)

Lastly, all-cause mortality, a serious adverse event, will be evaluated.

Relevant ICD codes and operational definition are provided in the Annex.

[figure not shown]
For the analysis of the primary outcome, individuals will be followed up from the index date until the earliest of the following

- 1) Outcome of interest
- 2) disenrollment;
- 3) the end of the study period;
- 4) death;
- 5) discontinuation of the index drug use as a lapse of 45 days without subsequent prescription;
- 6) adding ICS mono on top of Tio/Olo.

Statistical and Epidemiological Analysis Plan (SEAP) for Non-Interventional Studies (NIS) Template

c40431892-01 Page 11 of 38

Proprietary confidential information © 2022 Boehringer Ingelheim International GmbH or one or more of its affiliated companies

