10. DATA ANALYSIS

10.1 MAIN ANALYSIS

All variables, including patient characteristics, baseline measures, and outcomes, will be analyzed descriptively.

- For all analyses, variables will be reported as follows: Continuous variables (e.g., age) will be presented as means (with standard deviation, SD) and/or medians (with interquartile range, IQR), minimum, maximum.
- Categorical variables (e.g., sex) will be presented as absolute and relative frequencies.

We will first describe formation of the study cohort. Patient characteristics at baseline will be described using standard descriptive statistics. Absolute standardized differences (ASDs) will be used to compare the characteristics between the two groups, in which a >0.1 ASD indicates a meaningful difference.

As an objective of the study was to compare the clinical attributes of patients in each study group. The standardized difference will be used as a parameter to quantify the between-group differences for each clinical attribute. This is metric is commonly used in studies utilizing

Statistical and Epidemiological Analysis Plan (SEAP) for Non-Interventional Studies (NIS) Template

c40431892-01 Page 15 of 38

Proprietary confidential information © 2022 Boehringer Ingelheim International GmbH or one or more of its affiliated companies

secondary health data, in which a standardized difference of larger than 0.1 indicates a meaningful difference with respect to the clinical attribute between the two study groups.

For the analysis of primary outcome, the incidence rates of AEs during entire follow-up period will be calculated based on the following formula:

(Total number of patients in the Tio+Olo cohort experiencing an event of interest for the first time during the given time period) / (Total person-time at risk from current use of Tio+Olo during the given period)

[figure not shown]
Number of at-risk patients will be defined for specific adverse outcome of interest, taking into account whether it is a chronic condition for which patients with a prevalent condition are not considered at risk.

For the analysis of the primary outcome, individuals will be followed up from the index date until the earliest of the following

- 1) Outcome of interest
- 2) disenrollment;
- 3) the end of the study period;
- 4) death;
- 5) discontinuation of the index drug use as a lapse of 45 days without subsequent prescription;
- 6) adding ICS mono on top of Tio/Olo.

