ANNEX 1. ADDITIONAL INFORMATION

Table 1. Demographic and cohort entry of the Tio/Olo cohort and LAMA/LABA cohort

	Tio/Olo cohort N=xxxx		LAMA/LABA coho N=xxxx	
	N	%	N	%
Gender				
Male				
Female				
Age				
Mean, SD				
40~59				
60~79				
80+				
Calendar year of cohort entry				
2014				
2015				
2016				
2017				
2018				
2019				
Season of cohort entry date				
Spring (Mar-May)				
Summer (Jun-Aug)				
Fall (Sep-Nov)				
Winter (Dec-Feb)				

Statistical and Epidemiological Analysis Plan (SEAP) for Non-Interventional Studies (NIS) Template

c40431892-01 Page 20 of 38

Table 2. Incidence rate of adverse events in patients with COPD treated with Tio+Olo

Adverse event	No. of events	Person-Years	Incidence rate (per 100 000 person year)	95% CI
Potentially recurrent events				
Nasopharyngitis				
Pneumonia				
Moderate COPD exacerbation				
Severe COPD exacerbation				
Constipation				
Diarrhoea				
Urinary retention				
Urinary tract infection				
Urticaria				
Rash				
Incident events (no occurrence o	f corresponding	g codes during t	the 1-year baselin	ie period)
Arrhythmia				
Myocardial ischemia				
Supraventricular tachycardia				
Glaucoma				
Nonfatal myocardial infarction				
Nonfatal hemorrhagic stroke				
Nonfatal ischemic stroke				
Nonfatal Acute, but ill-				
defined, cerebrovascular				
disease				
Death				

Statistical and Epidemiological Analysis Plan (SEAP) for Non-Interventional Studies (NIS) Template

c40431892-01 Page 21 of 38

Table 3. Secondary outcome (baseline comparison between two study groups)

- ,		1			J & 1)
	Tio/Ol/	o cohort	LAM	A/LABA	
		XXXX	со	hort	Standardized
			N=	XXXX	difference
	N	%	N	%	
COPD treatments in 1 year prior to inde	ex date				
LAMA					
LABA					
ICS					
ICS+LABA free combination					
ICS+LAMA free combination					
LAMA+LABA free combination					
ICS+LAMA+LABA free combination					
ICS/LABA FDC					
LAMA/LABA FDC					
ICS/LAMA/LABA FDC					
Use of other respiratory drugs in 1 year	prior to	index			
date					
Mucolytics					
Theophylline					
Short-acting beta-agonists (SABA)					
Short-acting muscarinic antagonists					
(SAMA)					
Acute COPD exacerbation in 1 year prior	or to inde	x date			
Moderate exacerbation					
0					
1					
>=2					
Severe exacerbation					
0					
1					
>=2					
All exacerbations (Moderate +					
Severe)					
0					
1 >=2					
	c prior to	indov			
Acute COPD exacerbation in the 30 day date	s prior to	inuex			
Moderate exacerbation					
0 1					
>=2					

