Appendix 3. ICD codes and operational definition of adverse events

	Adverse events	ICD codes	Operational definition
1	Nasopharyngitis	ICD9: 472.2, 460 ICD10: J31.1, J00	Inpatient or outpatient (including ER visit) diagnosis.
2	Pneumonia	ICD9: 480-486, 487.0 ICD10: J10.0, J11.0, J12- J18,	 Primary inpatient diagnosis Inpatient diagnosis.
3	Moderate COPD exacerbation	ICD9: 491.x, 492.x, 496 ICD10: J41.x, J42, J43.x, J44.x	Outpatient diagnosis plus a prescription for oral corticosteroid or antibiotic for respiratory infection
4	Severe COPD exacerbation	ICD9: 491.x, 492.x, 496 ICD10: J41.x, J42, J43.x, J44.x	Inpatient or ER visits with a primary diagnosis.
5	Arrhythmia	ICD9: 427.x ICD10: I47.x, I48.x, I49.x	Inpatient or outpatient (including ER visit) diagnosis.
6	Myocardial ischemia	ICD9: 410.x, 411.x, 413.x ICD10: I20.x, I21.x, I22.x, I23.x, I24.x	Inpatient or outpatient (including ER visit) diagnosis.
7	Supraventricular tachycardia	ICD9: 427.0 ICD10: I47.1	Inpatient or outpatient (including ER visit) diagnosis.
8	Constipation	ICD9: 564.0, 564.00, 564.09 ICD10: K59.0, K59.00, K59.09	Inpatient or outpatient (including ER visit) diagnosis.
9	Diarrhoea	ICD9: 787.91 ICD10: R19.7	Inpatient or outpatient (including ER visit) diagnosis.
10	Urinary retention	ICD9: 788.2, 788.20, 788.29 ICD10: R33.x	Inpatient or outpatient (including ER visit) diagnosis.
11	Urinary tract infection	ICD9: 590, 595, 601, 604 ICD10: N10, N12, N15.1, N30.0, N30.8, N30.9, N41.0, N41.2, N41.3, N39.0	 Primary inpatient diagnosis Inpatient diagnosis. Either inpatient diagnosis or at least 2 outpatients (including ER visit) diagnosis; diagnostic interval within 30 days.
12	Urticaria	ICD9: 708.x ICD10: L50.x	Inpatient or outpatient (including ER visit) diagnosis.
13	Rash	ICD9: 782.1 ICD10: R21	Inpatient or outpatient (including ER visit) diagnosis.

Statistical and Epidemiological Analysis Plan (SEAP) for Non-Interventional Studies (NIS) Template

c40431892-01 Page 31 of 38

14	Glaucoma	ICD9: 365.x	Inpatient or outpatient
		ICD10: H40.x	(including ER visit) diagnosis
			from ophthalmologist.
15	Nonfatal myocardial	ICD9: 410.x, 411.x	1. Primary inpatient diagnosis
	infarction	ICD10: I21.x, I22.x, I23.x	+ hospital discharge
			without death certificates
			2. Inpatient diagnosis +
			hospital discharge without
			death certificates
16	Nonfatal hemorrhagic stroke	ICD9: 430, 431, 432.x	1. Primary inpatient diagnosis
		ICD10: 160.x, 161.x, 162.x	+ hospital discharge
			without death certificates

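### Constipation and urinary retention have no baseline exclusion, so a patient already under care for either counts as a first on-drug event, and the rate overstates new onset

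*SAP*

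**What the plan says.** SAP 7.2.1 splits the adverse events into two lists. For the acute, recurring list (nasopharyngitis, pneumonia, COPD exacerbation, constipation, diarrhoea, urinary retention, urinary tract infection, urticaria, rash), "all subjects will be evaluated, regardless of whether such events occurred during the one-year baseline period". For the chronic list (arrhythmia, myocardial ischemia, supraventricular tachycardia, glaucoma, nonfatal myocardial infarction, nonfatal stroke), "subjects who had diagnosis of the condition during the one-year baseline period will be excluded from the incidence of adverse event analysis".

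The Table 2 shell in Annex 1 keeps the same split. Constipation and urinary retention stand under "Potentially recurrent events", and the block for patients without baseline codes begins at arrhythmia.

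Appendix 3 defines constipation by "ICD9: 564.0, 564.00, 564.09 ICD10: K59.0, K59.00, K59.09" and urinary retention by 788.2, 788.20, 788.29 and R33.x. For both, one diagnosis at any inpatient, outpatient or emergency contact is enough. It asks for no second claim, new treatment or preceding code-free interval.

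SAP 10.1 counts patients "experiencing an event of interest for the first time during the given time period", divided by person-time on Tio+Olo, with follow-up from the index date. It removes prevalent patients from the risk set only where the condition is chronic.

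**The concern.** Either condition can be under continuing care when Tio+Olo is started, and continuing care produces repeat codes. With no baseline exclusion and a one-code definition, the first routine visit after the index date is indistinguishable from new onset.

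The primary objective is an incidence rate of safety outcomes, and the report goes to health authorities (protocol 11.3). In the visible text, adverse-event rates are planned for the Tio+Olo cohort only, so no comparator rate carries the same excess.

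The Tio+Olo entry criteria exclude earlier use of the combination but not of a LAMA alone, which Table 3 lists as a baseline treatment. Some pre-index codes may therefore have arisen on earlier treatment.

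**Working it through.** **The plan's own figure.** Protocol Table 1 is the only quantitative planning figure. With 4000 patients entering uniformly over 6 years, person-time is 4000 × 3 = 12,000 years. Arrhythmia at 1.82 per 100 gives 0.0182 × 12,000 = 218.4 expected events. The 2.5% and 97.5% Poisson quantiles divided by 12,000 give 1.583 to 2.067 per 100, as printed. The other three rows also reproduce to three decimals. The table is not in dispute, but it has no row for constipation or urinary retention.

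**Tracing one patient through the rules.** Take a patient coded in the baseline year and again at a follow-up visit while on drug.

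- Urinary retention: stays in the risk set (7.2.1); the single code meets Appendix 3; it is the first in follow-up (10.1). Counted as an event.
- Glaucoma, same history: removed from the risk set (7.2.1). Not counted.

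The chronic-condition sentence in 10.1 does not alter the first result, because neither 7.2.1 nor Table 2 classes retention or constipation as chronic.

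**Size, on assumed inputs.** The documents give no baseline prevalence, re-coding frequency, new-onset rate or on-drug time for these outcomes. All four inputs below are assumptions.

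- p = share coded at baseline, 0.02 to 0.15
- r = their on-drug coding rate, 0.5 to 1.5 per year
- h = true new-onset rate in the others, 0.03 per year
- c = 1/T, the rate of leaving follow-up, with mean on-drug time T = 0.5 to 1 year (exponential)

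Events per patient: E = p·r/(r+c) + (1−p)·h/(h+c).
Person-years per patient: Y = p/(r+c) + (1−p)/(h+c).
Reported rate = E/Y. Share from baseline-coded patients = [p·r/(r+c)]/E.

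Low end (p = 0.02, r = 0.5, T = 1, c = 1):
E = 0.02 × 0.5/1.5 + 0.98 × 0.03/1.03 = 0.00667 + 0.02854 = 0.03521
Y = 0.02/1.5 + 0.98/1.03 = 0.01333 + 0.95146 = 0.96479

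High end (p = 0.15, r = 1.5, T = 0.5, c = 2):
E = 0.15 × 1.5/3.5 + 0.85 × 0.03/2.03 = 0.06429 + 0.01256 = 0.07685
Y = 0.15/3.5 + 0.85/2.03 = 0.04286 + 0.41872 = 0.46158

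| p | r | T | Rate per 100 PY | Ratio to 3.0 | Share from baseline-coded |
|---|---|---|---|---|---|
| 2% | 0.5 | 1 | 3.65 | 1.2 | 19% |
| 5% | 0.5 | 1 | 4.64 | 1.5 | 38% |
| 10% | 1.5 | 0.5 | 11.90 | 4.0 | 76% |
| 15% | 1.5 | 0.5 | 16.65 | 5.5 | 84% |

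(Ratios are from unrounded rates.)

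The ratio exceeds 1 whenever r is greater than h, so the direction is upward if baseline-coded patients are coded on drug more often than others acquire the condition. A wider set of assumptions (2% to 20% coded, 1 to 4 visits a year, new onset 2 to 5 per 100 PY, 0.5 to 3 years on drug) gives ratios from 1.11 to 16.45. The size is simply not pinned down.

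**Precision of a restricted row.** Relative interval width goes roughly as 1/√events. Dropping 19% of events widens it by 1/√0.81 = 1.1. Dropping 84% widens it by 1/√0.16 = 2.5.

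**The case against.** The rule is an open choice. 7.2.1 states it, 10.1 ties at-risk status to chronicity, and the Table 2 heading tells the reader that these rows are not limited to new cases. Recurrence or worsening on treatment in someone with a history is safety information, and a one-year exclusion would discard it. The model also treats every on-drug event in a baseline-coded patient as carry-over, although some will be genuine recurrences after an episode that had resolved. All of this stands. It argues for keeping the all-patients row and against moving the conditions to the chronic list. It does not make that row a measure of new onset.

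Text that is not visible may also matter. The checklist in protocol Annex 2 refers to a section 9.7.2 for stratified and sensitivity analyses, and the visible SAP passes from 10.1 to 10.3. A baseline-restricted analysis could be there, so the request is conditional.

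Three stronger readings are tempting and are not supported:

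- A reader might infer that these rates mostly reflect prior prevalence. Under the assumptions above, the share from baseline-coded patients runs from 19% to 84%.
- A reader might infer that the rates cannot be set against those of the randomised trials. The documents do not say how the trials counted patients with a history, and the visible text plans no such comparison for these events.
- A reader might take the nasopharyngitis list, "ICD9: 472.2, 460 ICD10: J31.1, J00", as proof that a chronic condition is included. Appendix 3 prints no code titles, so the documents alone do not show it.

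Nor is there a case for a blanket 30-day code-free rule for the other acute events. The third urinary tract infection definition needs at least two outpatient diagnoses within 30 days. If the event were dated at the confirming visit, such a rule would remove those outpatient cases.

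**Conclusion.** The point holds for constipation and urinary retention. As specified, pre-existing cases with a coded visit on drug enter the primary outcome as first events, so the rate is biased upward as a measure of newly arising events. That follows from the text, given only that such patients are re-coded more often than others develop the condition. The factor of about 1.2 to 5.5 is an illustration that rests wholly on the assumed prevalence, re-coding rate, true rate and on-drug time. It should not be quoted as an estimate for this study. The classification itself is defensible. What the visible plan lacks is a figure that can be read as new-event incidence.

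**What to change.** In SAP 7.2.1 and the Table 2 shell, keep the existing all-patients rows. For constipation and for urinary retention, add a row restricted to patients with no corresponding code in the one-year baseline period. State that the restricted row is the one to be interpreted as incidence of new events and that the all-patients row also includes continuing and recurrent cases. The same extra row may be added for nasopharyngitis. If a section not visible here already provides this, a cross-reference from 7.2.1 is enough.

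The cost is a few lines of wording, two or three table rows and reuse of the baseline flag already needed for the chronic list. No information is lost. The restricted rows will hold fewer patients and events, so their intervals will be wider, and possibly much wider if most events come from patients coded at baseline.

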7.2.2 Secondary outcomes

These are not "outcomes" that occurred after the index date in most studies. These are analysis of baseline characteristics of patients who initiated Tio+Olo or other LAMA/LABA.

Basic characteristics:

• Sex

Statistical and Epidemiological Analysis Plan (SEAP) for Non-Interventional Studies (NIS) Template

c40431892-01 Page 12 of 38

Proprietary confidential information © 2022 Boehringer Ingelheim International GmbH or one or more of its affiliated companies

- Age
- Calendar year of cohort entry
- Season of index date (winter, Dec-Feb; spring, Mar-May; summer, Jun-Aug; fall, Sep-Nov)

Additional characteristics will be defined during the 1-year pre-index baseline period:

- Specific previous COPD treatments
 - > LAMA monotherapy
 - ➤ LABA monotherapy
 - ➤ ICS monotherapy
 - LAMA/ICS combination therapy on the same day
 - ➤ LAMA+LABA free combinations and fixed dose combination
- Use of other respiratory drugs
 - Mucolytics
 - > Theophylline
 - Short-acting beta-agonists
 - Short-acting muscarinic antagonists
- Previous acute COPD exacerbation (measured both 12 months and in the 30 days prior to cohort entry), categorized as 0, 1, or 2+.
 - ➤ All exacerbations (Moderate + Severe)
 - An outpatient visit with a diagnosis code for COPD in any field + a prescription for an oral corticosteroid or an antibiotic for respiratory infections (Moderate); prescriptions within 30 days of each other were considered as continuation of the initial exacerbation.
 - ➤ Hospitalizations or emergency room visits with a primary diagnosis for COPD (Severe); hospitalizations or emergency room visits within 30 days of each other were considered as continuation of the initial exacerbation.
- Hospitalizations caused by exacerbation of COPD in 12 months prior to index date:
 - \triangleright 0;
 - **>** 1;
 - >=2:
- All-cause hospitalizations in 12 months prior to index date;
- Comorbidities:
 - Cardiovascular disease
 - Cerebrovascular disease
 - Diabetes
 - Chronic kidney disease
 - Pneumonia
 - > Cancer
 - Cirrhosis
- Charlson Comorbidity Index (CCI)

Statistical and Epidemiological Analysis Plan (SEAP) for Non-Interventional Studies (NIS) Template c40431892-01 Page 13 of 38

Proprietary confidential information © 2022 Boehringer Ingelheim International GmbH or one or more of its affiliated companies

- History of medications dispensed in the 12 months before or on the index date will be identified from the pharmacy dispensing history:
 - > Cardiovascular drugs: antihypertensives, antiarrhythmics, nitrates, heart failure medications
 - > Lipid-lowering medications
 - ➤ Blood glucose-lowering medications
 - Anticoagulants and antiplatelet agents
 - > Antibiotics
 - > Antineoplastic agents

Relevant ICD codes, drugs ATC codes and operational definition are provided in the Annex.

7.3 COVARIATES

Covariates are the same as that listed under 7.2.2.

8. DATA SOURCES

Data sources include Taiwan National Health Insurance (NHI), Taiwan Cancer Registry (TCR) and Taiwan Mortality Data. Taiwan Department of Statistics, Ministry of Health and Welfare is the unit designated by the government to manage health and social welfare statistical databases, and to develop data platform for academic research. Through the services provided by the Health and Welfare Data Science Center (HWDSC) of the Department of Statistics, researchers may access a wide range of health and welfare data, including claims, mortality (with cause of death) and Taiwan Cancer Registry (TCR). The HWDSC staff encrypt the national ID for all individuals according to a secure encryption algorithm that is not made known to the public. The encrypted ID is unique for all individuals and will be used for linkage between databases.

The ICD-9-CM coding system was used until the end of 2015 and the use of ICD-10-CM codes started on January 1, 2016.

9. DATA MANAGEMENT AND SOFTWARE/TOOLS

Statistical and Epidemiological Analysis Plan (SEAP) for Non-Interventional Studies (NIS) Template c40431892-01 Page 14 of 38

Proprietary confidential information © 2022 Boehringer Ingelheim International GmbH or one or more of its affiliated companies

9.1 **SOFTWARE/TOOLS**

All analysis will be conducted by SAS software version 9.4 (

9.2 HANDLING OF MISSING VALUES

As administrative data routinely submitted to the health authority, there are no missing value in the health insurance claims. Handling of apparently inconsistent data is described under section 9.3. The small number of subjects with missing information on date of birth or gender will be excluded from the study and described in Figure 1.

9.3 HANDLING OF INCONSISTENCIES IN DATA AND OUTLIERS

No clinical parameter values (such as blood pressure or laboratory examination results) are available, therefore potential outliers of continuous variables are not a major concern. Apparently inconsistent data, such birth year of 1860 or Tio+Olo prescriptions during the years that it was not covered, would be identified and subjects with inconsistent data will be excluded from analysis and described in Figure 1.

10. DATA ANALYSIS

10.1 MAIN ANALYSIS

All variables, including patient characteristics, baseline measures, and outcomes, will be analyzed descriptively.

- For all analyses, variables will be reported as follows: Continuous variables (e.g., age) will be presented as means (with standard deviation, SD) and/or medians (with interquartile range, IQR), minimum, maximum.
- Categorical variables (e.g., sex) will be presented as absolute and relative frequencies.

We will first describe formation of the study cohort. Patient characteristics at baseline will be described using standard descriptive statistics. Absolute standardized differences (ASDs) will be used to compare the characteristics between the two groups, in which a >0.1 ASD indicates a meaningful difference.

As an objective of the study was to compare the clinical attributes of patients in each study group. The standardized difference will be used as a parameter to quantify the between-group differences for each clinical attribute. This is metric is commonly used in studies utilizing

Statistical and Epidemiological Analysis Plan (SEAP) for Non-Interventional Studies (NIS) Template

c40431892-01 Page 15 of 38

Proprietary confidential information © 2022 Boehringer Ingelheim International GmbH or one or more of its affiliated companies

secondary health data, in which a standardized difference of larger than 0.1 indicates a meaningful difference with respect to the clinical attribute between the two study groups.

For the analysis of primary outcome, the incidence rates of AEs during entire follow-up period will be calculated based on the following formula:

(Total number of patients in the Tio+Olo cohort experiencing an event of interest for the first time during the given time period) / (Total person-time at risk from current use of Tio+Olo during the given period)

[figure not shown]
Number of at-risk patients will be defined for specific adverse outcome of interest, taking into account whether it is a chronic condition for which patients with a prevalent condition are not considered at risk.

For the analysis of the primary outcome, individuals will be followed up from the index date until the earliest of the following

- 1) Outcome of interest
- 2) disenrollment;
- 3) the end of the study period;
- 4) death;
- 5) discontinuation of the index drug use as a lapse of 45 days without subsequent prescription;
- 6) adding ICS mono on top of Tio/Olo.

Statistical and Epidemiological Analysis Plan (SEAP) for Non-Interventional Studies (NIS) Template

c40431892-01 Page 16 of 38

Statistical and Epidemiological Analysis Plan (SEAP) for Non-Interventional Studies (NIS) Template c40431892-01 Page 17 of 38

Proprietary confidential information © 2022 Boehringer Ingelheim International GmbH or one or more of its affiliated companies

